criteria and who are still willing to participate after completing the baseline assessment will be randomized to the intervention group or standard care group. All participants will complete two post-tests; post 1 will occur at approximately 9-10 weeks after enrollment (or 1-2 weeks after completion of the intervention for participants in the intervention group), and post 2 will occur approximately 12-13 weeks after post-test 1. The post-test assessments will include the same tools used in the baseline data collection. In addition, at both post-tests we will ask caregivers to disclose any resources they may have used during the duration of the study. At the 12 week post-test assessment the data collector will also ask questions on the Bakas “Enactment” tool to obtain data concerning the caregivers’ perceptions of the intervention. The data collector, who will be blinded to the group assignment of the caregivers, will telephone the caregivers to obtain the post-test assessments. We will obtain data on healthcare utilization since baseline assessment from the MCAS the Decision Support System National Data Extracts (DSS NDE) and the Non-VA Medical Carefee-basis files. Team members abstracting data from CPRS will be trained and inter-rater reliability testing will be conducted for all data collectors. We will conduct the assessments and intervention sessions at times that are convenient to the caregivers. All caregivers will receive reimbursement for their participation in the study.

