**Aim #1 - Hypothesis #1 (primary):** Stroke caregivers who receive the intervention will have less depressive symptoms at 1 and 12 weeks post-intervention compared to stroke caregivers in the standard care group. Our primary endpoint is the caregiver depressive score. The focus of the primary analysis will be to examine the effect of the intervention based on “intention to treat.” Data from all the participants will be part of the primary analyses regardless of actual number of completed sessions. As an exploratory study element, we will assess compliance and attempt to determine its effect on study results. For the primary analysis, the general linear mixed model for repeated measures will be used to model the follow-up depression times (1 and 12 weeks post-intervention), adjusted for baseline scores as fixed effects. Let  $y_{ij}$  be the depression score for person  $i$  at time  $j$ , then basic fixed effects model will be:

$$E(y_{ij}) = \beta_0 + \beta_1 \text{Baseline}_i + \beta_2 \text{Time}_{ij} + \beta_3 \text{Group}_i + \beta_4 \text{Group}_i * \text{Time}_{ij}$$

with covariates for baseline depression (Baseline), time (Time=0 for 1 week, 1 for 12 weeks post-intervention), and group (0 if active control, 1 if intervention). In order to control for possible chance sample imbalances resulting from randomization, the model will include covariates for baseline prognostic factors (e.g., discharge from hospital, community living center, or rehabilitation facility; caregivers’ relationship to Veteran; number of previous strokes among Veterans, etc.), deemed to have significant relationships with response and groupwise imbalances. Thus, analyses will be able to compare the groups on the measure of interest while controlling for these factors. The primary outcome of interest will be the immediate post-intervention effect at 1-week post-intervention with the 12-week post-intervention as a secondary outcome. This will be tested based on linear contrast  $\beta_3 + \beta_4$  at two-sided 0.05 level. All tests will be performed at the  $\alpha=0.05$  significance level. The correlation among observations from the same person will be accounted for through the inclusion of a random person effect into the mixed model analysis.

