**Aim #2 - Hypotheses #2 (secondary):** Stroke caregivers who receive the intervention will have superior outcomes (i.e., less burden, better problem solving skills, greater self-efficacy, and better HRQOL,) at 1 and 12 weeks post-intervention than caregivers in the standard care group. The analysis plan for Hypothesis 2 will closely follow the plan outlined above for Hypothesis 1 for each secondary outcome of interest.

**Aim #3 - Hypotheses #3 (secondary):** Veterans whose caregivers receive the intervention will have better functional abilities at 1 and 12 weeks post-intervention and less healthcare utilization at 12 weeks post-intervention measures compared to Veterans whose caregivers are in the standard care group. Since the score for the Stroke Impact Scale can be treated as a continuous, the analysis plan follows exactly as above in Hypothesis 1. Since the Veteran healthcare utilization measures are count data, the models will be a somewhat different. There will be no baseline covariates added to the model, as they are not applicable to the count measures. Analyses will be conducted for the period following baseline to 12 weeks post-intervention assessments. Generalized linear models for count data (such as Poisson or negative binomial regression models, depending on the presence or absence of over-dispersion) will be employed to determine the group effects on healthcare utilization. Log link functions will be employed on the count data to create the correct distributional data forms. As before, in order to control for possible sample imbalances resulting from randomization, all models will include covariates for prognostic factors deemed to have significant relationships with response and significant groupwise imbalances. Thus, analyses will be able to compare the groups on the measures of interest while controlling for these factors.

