To determine the intervention's impact on the costs of healthcare utilization, we will rely on ISPOR's 2014 budgetary impact analysis guidelines.[85] Data on VA utilization costs will be obtained from MCAS the Decision Support System National Data Extracts (DSS NDE) [86] and the Non-VA Medical Carefee-basis files.[87] We will tabulate all costs from these sources for study enrollees over the period of the study, calculate the difference between intervention and standard care average costs and test for the statistical significance of this difference using the Z-score method proposed by Zhou.[88] The final step in determining the budgetary

impact of the intervention will combine parts 1 and 2 to determine the complete impact of the intervention on the VA budget. While the incremental cost of the intervention (part 1) will be positive, the impact of the intervention on the costs of VA utilization will likely vary directly with the impact of the intervention on VA utilization.

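### The Aim 4 care-cost effect is an unadjusted difference of arm means, although baseline Veteran severity is collected; pre-specified adjustment would give a modest, nearly free gain in precision

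*Combined protocol and SAP*

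**What the plan says.** Section 6, Research Design and Methods Overview (Aims # 4), tabulates enrollees' costs from the VA and non-VA files over the study period. It will then "calculate the difference between intervention and standard care average costs" and "test for the statistical significance of this difference using the Z-score method proposed by Zhou". No covariate, baseline value or regression model appears anywhere in the Aim 4 text.

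The other aims are written differently, though not uniformly:

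- **Aim 1.** The depression model is "adjusted for baseline scores as fixed effects", and "the model will include covariates for baseline prognostic factors" where these are related to response and unbalanced between groups. Number of previous strokes is one of the examples given.
- **Aim 2.** "The analysis plan for Hypothesis 2 will closely follow the plan outlined above for Hypothesis 1 for each secondary outcome of interest".
- **Aim 3, Stroke Impact Scale.** "the analysis plan follows exactly as above in Hypothesis 1".
- **Aim 3, utilization counts.** The plan expressly adds no baseline covariate. It then says "all models will include covariates for prognostic factors deemed to have significant relationships with response and significant groupwise imbalances".

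Severity data exist at baseline. The Measures table lists the 16-item Stroke Impact Scale as a Veteran outcome, and under Data collection procedures "The post-test assessments will include the same tools used in the baseline data collection". The same paragraph has the number of previous strokes abstracted from the Veteran's record. The Randomization paragraph describes blocking over time and states no stratification by severity.

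**The concern.** Cost is likely to depend on how disabled the Veteran is. Neither the randomisation nor the Aim 4 analysis takes severity into account, so a chance difference in severity between the arms passes into the cost difference in proportion to how strongly severity predicts cost.

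The care-cost difference matters for the aim. The plan expects the intervention's own incremental cost to be positive, so only a saving in care costs can make the net budget impact negative. An interval wider than it need be makes that sign harder to establish. Adjusting a linear model for baseline measures in a randomised trial leaves the target, the difference in mean cost, unchanged.

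**Working it through.** **The plan's own figures.** The plan states no sample size, SD or precision for cost. Its one sample-size calculation is for the CES-D: 2 × (1.96 + 0.8416)² × (8.9/3.1)² = 129.4, so 130 per group, and 130/0.9 = 144.4, so 145. The stated 145 per group therefore reproduces, but it says nothing about cost. I use the planned total of 227.

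**Inputs.** N = 227 comes from the Sample Size paragraph. Everything about cost is assumed: lognormal costs with coefficient of variation CV (SD divided by mean) of 1.5 or 2, and baseline severity treated as one normally distributed score with correlation ρ of 0.2, 0.4 or 0.7 with log cost.

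**Step 1, raw standard error.** In units of the cost SD it is √(4/227) = 0.133. As a fraction of mean cost it is 1.5 × 0.1327 = 0.199 or 2 × 0.1327 = 0.265.

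**Step 2, correlation on the cost scale.** A linear term works on cost, not log cost. With σ² = ln(1 + CV²), the correlation of severity with cost is r = ρσ/CV.

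- CV 1.5: σ = √ln 3.25 = 1.086, so r = 0.724ρ.
- CV 2: σ = √ln 5 = 1.269, so r = 0.634ρ.

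**Step 3, adjusted standard error.** The ratio to the raw standard error is √[(1 − r²)(N − 2)/(N − 3)].

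| CV | ρ (log scale) | r (cost scale) | SE ratio | Reduction | Raw → adjusted SE (× mean cost) |
|---|---|---|---|---|---|
| 1.5 | 0.2 | 0.145 | 0.992 | 0.8% | 0.199 → 0.197 |
| 1.5 | 0.4 | 0.290 | 0.959 | 4.1% | 0.199 → 0.191 |
| 1.5 | 0.7 | 0.507 | 0.864 | 13.6% | 0.199 → 0.172 |
| 2 | 0.2 | 0.127 | 0.994 | 0.6% | 0.265 → 0.264 |
| 2 | 0.4 | 0.254 | 0.969 | 3.1% | 0.265 → 0.257 |
| 2 | 0.7 | 0.444 | 0.898 | 10.2% | 0.265 → 0.238 |

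For ρ from 0.4 to 0.7 the reduction is about 3% to 14%. That is equivalent to an unadjusted trial of about 242 (227/0.940) to 304 (227/0.747) Veterans.

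**Step 4, movement in one trial.** The 95% range of chance imbalance in a baseline covariate is ±1.96 × 0.133 = ±0.26 of its SD. At that limit the raw cost difference shifts by 1.96r of its own standard errors: about 0.5 at r = 0.254 and about 1.0 at r = 0.507.

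**Step 5, validity.** In 20,000 simulated trials with normal outcomes and no true effect, the raw test rejected 5.1% of the time at r = 0.3 and 5.3% at r = 0.5, and the mean estimate was essentially zero. In the 13% of trials where imbalance exceeded 0.2 SD, it rejected 8.7% and 13.6% of the time.

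**The case against.** The strongest reply is that nothing here is invalid. A difference of randomised means is unbiased, and its standard error already includes chance imbalance. The raised error rates in Step 5 hold only within the minority of trials with marked imbalance. Aim 4 is not the primary endpoint and has no precision target. The gain depends on a correlation that the documents do not give, and the eligibility rule (at least two ADL deficits, or a new or worsening neurological problem) may narrow the range of severity and so lower it. All of this stands. It limits the point to efficiency and to how the estimate behaves in the one trial run.

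Adjustment also has a cost. The Handling of Missing Data paragraph reports 0 to 10% missingness by measure in the pilot. Costs come from administrative files, so a complete-case regression could drop Veterans whose costs are known and offset a small gain. This stands too, and the fix has to deal with it.

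A reader might infer three stronger things that the documents do not support:

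- **That Aim 4 alone lacks adjustment.** The Aim 3 counts, the outcome nearest to cost, also get no baseline covariate. Prognostic factors enter those models only if related to response and significantly unbalanced, so severity is not assured a place there either.
- **That severity imbalance dominates the cost difference.** At the largest r used here, r² = 0.507² = 0.26, so about 74% of the variance of the raw difference has nothing to do with severity.
- **That adjusted Aim 3 and unadjusted Aim 4 results could conflict for no real reason.** Aim 3 counts unintended bed days, emergency visits and unscheduled clinic visits in log-link models. Aim 4 takes all costs, including pharmacy and laboratory, as a difference in means. They can differ for substantive reasons, and adjusting Aim 4 would not align them.

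**Conclusion.** The point holds as a modest, inexpensive improvement and not as an error. The Aim 4 estimator leaves out severity information that the trial collects. On the assumptions above (lognormal costs, SD 1.5 to 2 times the mean, one linear severity score), adjustment shortens the standard error by about 3% to 14% for log-scale correlations of 0.4 to 0.7, and by about 1% or less at 0.2. It also removes most of the shift due to whatever severity imbalance arises.

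It will not make the cost comparison precise. On the same assumptions, the raw difference detectable with 80% power is 2.80 × 0.199 = 0.56 to 2.80 × 0.265 = 0.74 of mean cost. In the best case shown, adjustment lowers the first figure to 0.56 × 0.864 = 0.48. Bias in the raw difference should not be inferred from any of this.

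**What to change.** In the Aim 4 analysis text, pre-specify the care-cost difference as the arm coefficient from a linear regression of total cost on randomised arm, baseline Stroke Impact Scale score and number of previous strokes. Give a robust or bootstrap 95% interval. Keeping the model linear on the cost scale keeps the estimate a difference in mean cost.

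Fill missing baseline covariates by a simple rule fixed in advance, such as the overall mean across both arms, so that no Veteran with known costs is dropped. Report the raw difference and its test beside the adjusted result.

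The cost is two or three sentences in the plan, the rule for missing baseline scores and slightly more analysis work. No new data are needed. Naming the covariates now also prevents their being chosen after costs have been seen.

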### **Research Design and Methods Overview (Aims # 5)**

**Aim #5: to determine the acceptability of the intervention and the facilitators and barriers that Spanish-speaking stroke caregivers perceive when participating in the study.**

**Research question #1: What are the caregivers' perceptions of the value, strengths/weaknesses of the intervention and what facilitators/barriers did they identify with the intervention?**

We will conduct in-depth, qualitative interviews with caregivers from the intervention group. Sample (size, recruitment, enrollment): Our sample will be 8-12 stroke caregivers. Sample size considerations in qualitative studies include the purpose/goal of the study and the depth of data needed to reach theoretical saturation and adequately answer the study question.[89,90] Typically, 8-12 participants are needed to reach theoretical sample.[91] We will select a purposive subsample of 8-12 caregivers who participated in the intervention arm of the project. To get a diversity of caregiver perceptions, we will use a maximum variation sampling technique[91] to select caregivers with high, medium, and low scores on the CES-D depression scale. We will sequentially enroll the caregivers following their completion of the intervention until we have the desired sample size. Data collection: The Spanish-speaking data collector will conduct the interviews over the telephone using an interview script. The data collector will ask caregivers' their perceptions of the value, strengths/weaknesses of the intervention, and about the barriers and facilitators in participating in the intervention. All qualitative interviews will be digitally recorded, transcribed verbatim, and validated by another Spanish-speaking member of the research team. Data analysis: We will employ a mixed methods, explanatory sequential design (i.e., collecting and analyzing quantitative and qualitative data in two consecutive phases). Quantitative and qualitative methods complement each other and when used in combination, they provide a more comprehensive explanation of the research question.[91] In the qualitative interviews, we will obtain information on the caregivers' perceptions of the intervention. The quantitative data obtained from the Enactment Tool (Bakas) in which the caregiver rates aspects of the intervention, combined with qualitative data, will help us understand which aspects of the website and intervention were most beneficial and how the perceptions about the strengths and weaknesses of the various parts of the intervention varied between caregivers with different depression levels. To assure rigor of our methods, we will adhere to recommendations of Lincoln and Egon[92]: 1) use multiple sources of data, 2) ask team members to independently analyze the data, 3) meet regularly to discuss coding and interpretation of the data, 4) maintain an audit trail of decisions made during the analysis, and 5) review field notes of the interviewer to identify factors that may influence data quality. Team members will begin by reading the first two caregiver transcripts to identify initial concepts and codes. Then, they will enter data labels and codes into NVivo, a software program that our team has purchased and used in previous projects. NVivo compiles data related to a code, groups related data, and provides a print out of all data for each code to assist further analysis. The team members involved in the qualitative analysis will regularly interact with other members of the research team to discuss and ultimately arrive at consensus about coding schemes. A final coding framework and codebook will be created. As the interviews are completed, we will continue coding and use an iterative, inductive process to generate categories and themes based on repetitive patterns in the data. Throughout the analysis, we will write memos in NVIVO about data analysis decisions. Common themes with selected, supportive quotations will be presented. We will triangulate the findings from the quantitative and qualitative data to interpret the findings. This analysis will answer our research question, help us disentangle which aspects of the intervention did or did not support our hypotheses, and provide data to refine methods for future testing and roll-outs.

Compensation: Participants will be compensated for their time and effort. Participants in both intervention and standard care group will receive \$15 for their time and effort for every data collection they complete for a total of \$45 if they complete all three. Twelve participants from the intervention group will receive an additional \$15 each for completing an individual interview. Compensation will be process either at the completion of the study or when a participant withdraws from the study.

The US Treasury requires that all participants in this study receive their study related compensation as an electronic transfer of money directly to their bank accounts. If caregivers are already set up to receive VA benefit

payments electronically, then there is nothing that they need to do. If they are not already set up to receive VA benefit payments directly to their bank accounts then they will need to set up an account to receive an electronic funds transfer from the VA. Study staff will provide information on this process, if needed.

Caregivers' compensation for participation in this research study will come from the VA Finance Office, who will issue payment to them by direct deposit to their bank account.

The participants may be responsible for paying income taxes on any payments provided by the study. Any payment made to caregivers on a VA-funded study, regardless of amount, has to be reported to the Internal Revenue Service (IRS) because the payment system cannot distinguish payment from reimbursement for expenses.

**Data Privacy, Confidentiality, and Safety:** The research team will protect the privacy of all study participants enrolled. These safeguards include conducting all the telephone interviews and data collection calls in a private and secure area. To safeguard the identity of study participants, immediately after enrolling in the study each participant will be assigned a subject code, starting with 001, that will be used instead of the participant's name. However, the names will be linked to the subjects' code. All data files in paper format will be kept in a secured location to be determined by the ACOR of R&D under double locks- a locked filing cabinet in a locked office and stored in password-protected computer files on a secure VA server only accessible to authorized members of the research team. All study related documents containing PHI will be de-identified by using the subjects' assigned code. No subjects will be identified by name in any reports. Only aggregated data will be submitted. Subjects will not be identified by their names on study documents, only by their subject code. A log for accounting disclosures will be kept as per Privacy guidelines. Electronic Data will be identified using subject's code and will be stored in an electronic folder in a restricted password protected folder under the link\\Vhasajsvr6\\group Folders\\Research Active Studies\\[name]\\[name], Spanish Online & Telephone Intervention for Caregivers of Veterans with Stroke in a VA network drive that undergoes regular backups. No data will be stored in the PC hard drive. The data collection, data flow and management will be as outlined in the proposal. A mobile device, a PHILLIPS-LFH 9600 digital pocket memo w/speech pro recorder will be used in this study to record the interviews. Digital files will be deleted from the recorded immediately after downloading them to the protected folder in the VA network (see above). These recorders are VA encrypted voice recorders. This recorder will be kept in a cabinet double locked in the PI office. A track of all sessions recorded will be maintained. The storage and disposition these recordings will be as per Record Control Schedule guidelines.

This study involves non-veterans subjects who will be enrolled in the study. Because we will not be providing any medical care as part of this educational study, we will document study participants' (i.e, Veterans' caregivers) participation on this study on their corresponding Veterans electronic chart. The Notice of Privacy Practice will be provided to the non-veterans subjects via mail and they must return the VA form 10-0483 signed to the PI or delegate.

This study does not involve use of any software that is not already in use within the VACHS. A web application (VA RESCUE website) will only be used to download educational information). All data will be treated confidentially and will be kept in locked files in a double locked offices at the office assigned for this study by the Research Service].

Data will not be removed from the VA protected environment. Only electronic data will be shared among members of the research team in Gainesville and PR. All paper study documents will be scanned into electronic format and shared between members of the research team via the study shared folder or encrypted VA email message. The study will share the electronic data via the assigned electronic study folder in a VA protected shared drive behind the VA firewall. Original documents and data derived from this research will be kept in an office to be assigned by the ACOS of R&D to securely store study documents behind double locks. Once the study is completed and regulatory audits have been completed, all data/documents will be returned to the

Research Administrative Office for disposition. The destruction of identifiers and records will be in accordance with VA Record Control Schedule.

If any of the study staff discontinues his/her participation in the study, the IRB will be notified by completing a "Change in Research Staff" document and his/her access to the study data will be removed. Any incident regarding information security and/or privacy will be reported in accordance with VA policy and procedures in place for reporting incidents as described in VACHS IRB SOP and ISO SOP.

